#### 8.3.2.2 Jugular Venous Distension, Hepatomegaly and Cardiothoracic Ratio

Descriptive statistics and two-sided 95% confidence intervals (based on t-distribution) will be calculated for measured values and changes from baseline at the time of final IMP administration. Descriptive statistics will also be calculated at each time point after IMP administration. Note that the absence of jugular venous distension and hepatomegaly will be indicated as 0 cm. The above data on jugular venous distension and hepatomegaly will also be summarized in the same manner for subjects with baseline value. For the presence of jugular venous distension and hepatomegaly, shift tables in changes from baseline at

the final IMP administration and at each time point following IMP administration will be prepared.

### **8.3.2.3 Pulmonary Rales and Cardiac Third Sound**

The number, and proportion with the two-sided 95% confidence intervals (exact) will be calculated for the resolution rates of pulmonary rales and cardiac third sound at the time of final IMP administration. The resolution rate is defined as the proportion of subjects in whom a symptom is present at baseline and disappears after IMP administration.

Shift tables showing whether the symptom is present will be prepared at each on-treatment time point and at the time of final IMP administration compared with baseline.

### **8.3.3 Dyspnea**

#### **8.3.3.1 Respiratory Rate**

Descriptive statistics and two-sided 95% confidence intervals (based on t-distribution) will be calculated for measured values and changes from baseline at the time of final IMP administration. At each time point, descriptive statistics will be calculated.

#### **8.3.3.2 Orthopnea and Paroxysmal Nocturnal Dyspnea**

The number, and proportion with the two-sided 95% confidence intervals (exact) will be calculated for the resolution rates of orthopnea and paroxysmal nocturnal dyspnea at the time of final IMP administration. The resolution rate is defined as the proportion of subjects in whom a symptom is present at baseline and then disappears after IMP administration.

Shift tables showing whether each symptom is present will be prepared at each postdose time point and at the time of final IMP administration compared with baseline.

#### **8.3.3.3 Subject-assessed Dyspnea**

The number, and proportion with the two-sided 95% confidence intervals (exact) will be calculated for the improvement rate at the time of final IMP administration. The improvement rate is defined as the proportion of subjects in whom a symptom is present at baseline and then mildly improved, moderately improved or markedly improved after IMP administration.

The frequencies at each postdose time point and at the time of final IMP administration will be summarized.

### **8.3.4 NYHA Classification**

A shift table showing the NYHA classification will be prepared at each on-treatment time point and at the time of final IMP administration compared to baseline.

For subjects in Class II and higher, the number and proportion with two-sided 95% confidence intervals (exact) will be calculated for subjects who have improved from baseline by 1 class or more at the final IMP administration.

### **8.4 Subgroup Analyses**

Subgroup analyses will not be performed in this trial.

## **9 Safety Analyses**

The following analyses will be conducted on the safety dataset. The same analyses will also be conducted for subjects categorized by the presence or absence of dose escalation (ie, subjects with dose increased to 16 mg and subjects with dose maintained at 8 mg without dose escalation) based on the dose escalation criteria.

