3.2 Trial Treatments

3.2.1 Dosage Regimen

The investigator or subinvestigator will administer OPC-61815 once daily as 1-hour infusion (55 to 70 minutes allowable) according to the IMP administration procedures specified separately. OPC-61815 treatment will start with 8 mg, and eligibility for dose escalation will be assessed on Day 2 of the treatment period (and again on Day 3 of the treatment period, if applicable) according to [Section 3.2.2](#). If the dose escalation criteria

are met, the dose will be increased to 16 mg; if the criteria are not met, administration will continue at 8 mg.

When AEs associated with the aquauretic effect of OPC-61815 including hypernatremia, dehydration, and thirst occur or worsen after the dose is increased to 16 mg and dose reduction is judged to be necessary by the investigator or subinvestigator, the dose will be returned to 8 mg. The dose may not be re-escalated to 16 mg once it has been reduced to 8 mg. The start time of administration on Day 2 and onward should coincide roughly (\pm 1 hour, whenever possible) with the start time on Day 1.

A flowchart of the dose escalation decision is presented in [Figure 3.2.1-1](#).

[figure not shown]

Figure 3.2.1-1 Flowchart of the Dose Escalation Decision

^aWhen only No. 2 of the Day 2 dose escalation criteria is not met

^bWhen any of No. 1, 3, or 4 of the Day 2 dose escalation criteria are not met

^cWhen AEs associated with the aquauretic effect of OPC-61815 including hypernatremia, dehydration, and thirst occur or worsen, and dose reduction is judged to be necessary by the investigator or subinvestigator

The following information will be recorded in the source document and the electronic case report form (eCRF).

- Times and dates at which OPC-61815 intravenous administration is started and ended (and suspension period, if the administration is suspended)
- Dose

- If eligibility for dose escalation is assessed, the result (date of assessment, and whether or not each criterion is met)
- If the dose is reduced, the AE(s) leading to dose reduction

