3.2.2 Dose Escalation Decision

1) Predose on Day 2

When all (No. 1 to No. 4) of the Day 2 dose escalation criteria ([Table 3.2.2-1](#)) are met, the dose will be increased to 16 mg.

When any of the following criteria are not met, the dose for Day 2 and onward will remain at 8 mg, and dose escalation assessment will not be repeated at predose on Day 3.

- No. 1 of the Day 2 dose escalation criteria
- No. 3 of the Day 2 dose escalation criteria
- No. 4 of the Day 2 dose escalation criteria

Table 3.2.2-1 Day 2 Dose Escalation Criteria	
1	An adequate response is absent (when either of the following is met). 
 1) When the increase in daily urine volume from baseline (the daily urine volume through immediately predose on Day 1) is ≤ 500 mL: Any congestive symptom (lower limb edema, hepatomegaly, jugular venous distension, cardiothoracic ratio, pulmonary rales, or cardiac third sound) is present. 2) When the increase in daily urine volume from baseline (the daily urine volume through immediately predose on Day 1) is > 500 mL or cannot definitely be concluded to be ≤ 500 mL: Body weight did not decrease as compared with predose on Day 1 with no improvement in congestive symptoms.
2	The serum sodium concentration at predose on Day 2 is ≤ 147 mEq/L. ^a
3	An increase of > 10 mEq/L in serum sodium concentration is not evident within 24 hours after start of IMP administration on Day 1. ^a
4	No safety concerns have arisen since the start of IMP administration on Day 1 at the discretion of the investigator or subinvestigator.

^aIf serum sodium concentration measurement is difficult to perform at the trial site, plasma sodium concentrations will be used for the assessment.

2) Predose on Day 3

When only No. 2 of the Day 2 dose escalation criteria was not met, eligibility for dose escalation will be reassessed on Day 3 according to the Day 3 dose escalation criteria ([Table 3.2.2-2](#)).

When all (No. 1 to No. 4) of the Day 3 dose escalation criteria are met, the dose will be increased to 16 mg. When any of the Day 3 dose escalation criteria are not met, the dose for Day 3 onward will remain at 8 mg.

Table 3.2.2-2 Day 3 Dose Escalation Criteria

1	An adequate response is absent. 1) Body weight did not decrease as compared with predose on Day 2 with no improvement in congestive symptoms.
2	The serum sodium concentration at predose on Day 3 is ≤ 147 mEq/L. ^a

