3	An increase of >10 mEq/L in serum sodium concentration is not evident within 24 hours after the start of IMP administration on Day 2. ^a
4	No safety concerns have arisen since the start of IMP administration on Day 2 at the discretion of the investigator or subinvestigator.

^aIf serum sodium concentration measurement is difficult to perform at the trial site, plasma sodium concentrations will be used for the assessment.

[Rationale for the Day 2 dose escalation criteria]

1. The results from the OPC-61815 8-mg group, the OPC-61815 16-mg group, and the tolvaptan 15-mg group of the phase 2 clinical pharmacology trial (Trial 263-102-00001) showed that the mean changes in body weight from baseline to the day after the final IMP administration of 5-day treatment were -2.0 kg and -1.1 kg, respectively, in subjects with a >500 mL change in daily urine volume from baseline to Day 2 (from the start of administration on Day 1 to predose on Day 2) and in those with a ≤ 500 mL change. This finding suggested that the decrease in body weight (the primary efficacy endpoint in the present trial) might be smaller in subjects in whom the change in daily urine volume from baseline to Day 2 was as small as ≤ 500 mL.

However, in some of the subjects with a >500 mL increase in daily urine volume from baseline to Day 2, body weight did not decrease from the previous day with no improvement in congestive symptoms, suggesting an insufficient improvement of volume overload; therefore, this criterion is set to enroll such subjects as well.

2. This criterion is set because the upper limit of reference range of serum sodium concentration is 147 mEq/L.
3. In the treatment of hyponatremia, there is a concern regarding the increased risk of osmotic demyelination syndrome due to a rapid increase in serum sodium concentration, and an alert has been indicating that the increase in serum sodium concentration should be ≤ 10 mEq/L per 24 hours; therefore, this criterion is set.

4. This criterion is based on safety considerations.

[Rationale for the Day 3 dose escalation criteria]

1. No decrease in body weight combined with no improvement in congestive symptoms as compared with the previous day is considered to indicate an insufficient improvement in volume overload; therefore, this criterion is set.

2 to 4. Same as the Day 2 dose escalation criteria

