### **3.4 Handling of Time Points**

Case report form (CRF) Visit values at each time point (time points from baseline in the screening, treatment, and follow-up periods as specified in the protocol Table 3.7.1) will be used in summaries (but values at the time of discontinuation will not be used in summaries). Unscheduled Visit values will not be used.

According to the rules specified in the protocol [Section 3.2.3](#), for the completion assessment of subjects who have completed treatment after a treatment period of shorter than 5 days, the CRF Visit will be set to correspond with the day of assessment for the analysis visit. Concerning interval urine samples, the daily urine volume will be calculated by summing all the interval urine volumes that constitute the daily urine volume for that day. If the interval urine sample is the last one for that day, the corresponding interval will be set as the analysis interval. The same rules also apply to fluid intake and urine electrolyte excretion. Other variables specified in the corresponding CRF Visit to be measured multiple times will be set to precede IMP administration.

Baseline and final administration time point for each variable are defined as follows.

Table 3.4-1 Handling of Time Points		
Variable	Baseline	Final Administration Time Point
Clinical laboratory value	Before IMP administration on Day 1	Day after final IMP administration
Vital signs	Before IMP administration on Day 1 (Screening values will be used if the values at screening are measured on Day 1 but not measured prior to the IMP administration on that day.)	Day after final IMP administration
12-lead ECG	Before IMP administration on Day 1	Day after final IMP administration
Daily urine volume, daily fluid intake, daily fluid balance	Within 24 hours before IMP administration on Day 1	-
Serum sodium concentration, serum potassium concentration, serum osmolality	Before IMP administration on Day 1	-
Daily urine sodium excretion, daily urine potassium excretion	Within 24 hours before IMP administration on Day 1	-
Urine osmolality	Within 24 hours before IMP administration on Day 1	-
Biomarkers (plasma AVP concentration, plasma renin activity, plasma brain natriuretic peptide [BNP] concentration, serum N-terminal pro-brain natriuretic peptide [NT-proBNP] concentration, and serum troponin I concentration)	Before IMP administration on Day 1	Day after final IMP administration

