### **9.2 Adverse Events**

All AEs will be coded by system organ class (SOC) and ICH Medical Dictionary for Regulatory Activities (MedDRA) preferred term (PT). The incidence of the following events will be summarized for all events, by SOC, and by PT.

- Treatment-emergent AEs (TEAEs)
- TEAEs by severity
- TEAEs with an outcome of death
- Serious TEAEs
- TEAEs leading to discontinuation of the IMP

If there are multiple occurrences of the same event in the same period in the same subject, the event with the highest severity will be selected. IMP-related TEAEs will be summarized in the same manner as shown above.

For TEAEs, a summary table will also be created for any TEAE that occurs in more than 2 subjects in any group.

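### The by-escalation safety split in SAP 9 counts events that began at 8 mg in the escalated group, and no planned AE or sodium-event table is by dose at onset

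*SAP*

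**What the plan says.** Dosing (Protocol 3.2.1 to 3.2.3). Treatment starts at 8 mg and lasts at most 5 days. Before the Day 2 dose, four criteria are checked: inadequate response (No. 1), sodium at or below 147 mEq/L (No. 2), no rise above 10 mEq/L after the Day 1 dose (No. 3) and no safety concern (No. 4). For Nos. 1, 3 and 4 the rule is: "When any of the following criteria are not met, the dose for Day 2 and onward will remain at 8 mg". The one route to a later increase is: "When only No. 2 of the Day 2 dose escalation criteria was not met, eligibility for dose escalation will be reassessed on Day 3". On No. 2 the protocol explains: "This criterion is set because the upper limit of reference range of serum sodium concentration is 147 mEq/L". If AEs linked to the aquaretic effect lead to a dose reduction after escalation, "the dose will be returned to 8 mg".

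Analysis. SAP 9 runs the safety analyses on all treated subjects and adds: "The same analyses will also be conducted for subjects categorized by the presence or absence of dose escalation". SAP 9.2 counts TEAEs by SOC and PT, with no rule on dose at onset. SAP 9.3 counts subjects with sodium above 147 mEq/L, or a rise above 10 mEq/L within 24 hours, at any time after dosing, from central laboratory values. In SAP Appendix 1, only the exposure tables CT-7.1.2 and CT-7.1.3 are by dose among the safety tables. SAP 14 replaces the protocol's three groups (escalated on Day 2, on Day 3, or not at all) with two, because the distribution of subjects differed from what was expected. It gives no counts.

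**The concern.** The objective (Protocol 2.3, SAP 2) is tolerability at 8 or 16 mg, and Protocol 2.1 names hypernatremia and dehydration as the main worries in patients who cannot drink. A reader who wants to know what happened at 16 mg will turn to the escalated group in the AE tables and CT-10.6. That group also holds everything that happened to the same subjects at 8 mg, both before escalation and after any reduction. The summary tables do not show which of those events began at 16 mg.

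The Day 3 route makes this concrete for sodium. It is open only to subjects whose sodium exceeded 147 mEq/L after the first 8 mg dose, and CT-10.6 counts that same threshold.

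**Working it through.** **The plan's own figure.** With 40 subjects, the chance of at least one event is 1 − (1 − p)^40. This gives 87.1% at p = 0.05 and 80.5% at p = 0.04, which matches the stated 87% and 80%. Those figures apply to all 40 subjects and are not affected by this point.

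**Share of dosing days at 8 mg before escalation.** For escalation on day k and five dosing days without reduction, the share is (k − 1)/5:

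- Day 2: 1/5 = 20%.
- Day 3: 2/5 = 40%.

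AEs are also collected up to follow-up, 7 to 10 days after the last dose. With a last dose on Day 5 that is Day 12 to Day 15. If follow-up time is assigned to the last dose, the shares become:

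- Day 2: 1/15 to 1/12, or about 7% to 8%.
- Day 3: 2/15 to 2/12, or about 13% to 17%.

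**From days to events (illustration).** Assume a constant daily first-event risk h, equal at both doses, and count on-treatment events only. Five-day incidence is F = 1 − (1 − h)^5. The part that begins before escalation is 1 − (1 − h)^(k − 1). At F = 20%, h = 1 − 0.8^(1/5) = 4.36%:

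- Day 2 escalator: 4.4 of the 20 points, or 22% of subjects with an event, had first onset at 8 mg.
- Day 3 escalator: 1 − 0.8^(2/5) = 8.5 points, or 43%.

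Over F = 10% to 50%, the shares run from 21% to 26% (Day 2) and from 41% to 48% (Day 3).

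**Where the 8 mg experience is reported.** The number escalated is not given. Assume E of 40 escalate and all are dosed for 5 days. The fraction of all 8 mg dosing days that falls in the escalated group is E(k − 1) / [5(40 − E) + E(k − 1)].

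| E | All on Day 2 | All on Day 3 |
|---|---|---|
| 10 | 10/160 = 6% | 20/170 = 12% |
| 20 | 20/120 = 17% | 40/140 = 29% |
| 30 | 30/80 = 38% | 60/110 = 55% |

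**Sodium above 147 mEq/L.** Each Day 3 escalator whose central value agrees with the site value enters CT-10.6 through an event at 8 mg. As a share of the escalated group this is 1/E: 10.0, 5.0 or 3.3 percentage points for E = 10, 20 or 30. The contribution is zero if nobody escalated on Day 3. It changes no count if the subject also exceeds 147 mEq/L at 16 mg, because the table counts subjects.

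**After a return to 8 mg.** Events in this phase also stay in the escalated group. The documents give no number of reductions, so this part cannot be sized.

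**The case against.** The strongest reply is that the SAP's group labels describe subjects accurately. It never says that events in the escalated group are due to 16 mg, and it claims no dose comparison. The trial studies an 8-to-16 mg titration, has no control group and sets no primary or secondary outcome variables. The all-subject tables carry the main result. With 40 subjects, the AE, compliance and dose-increase listings (AE-1, SMED-1, PDATA-16) allow tracing by subject. The sodium shift tables (CT-10.3.2) and SAP 11.2 show part of the sodium picture. All of this stands and limits the weight of the point. What remains is that no planned summary gives AE or CT-10.6 incidence by dose at onset.

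Four stronger readings are tempting, and the documents do not support them:

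- **Rises above 10 mEq/L are misplaced in the same way.** Criterion 3 is that such a rise "in serum sodium concentration is not evident within 24 hours after start of IMP administration on Day 1". A Day 1 rise therefore bars escalation and normally falls in the maintained group, at the correct dose. That is selection, not misplacement.
- **CT-10.6 may use predose values only.** SAP 3.4 says "Other variables specified in the corresponding CRF Visit to be measured multiple times will be set to precede IMP administration", but this closes a paragraph on mapping visits for subjects who complete early, and most naturally belongs there. SAP 11.2 still summarises sodium at each time point on the escalation day, where 4-hour and 8-hour samples are scheduled.
- **The AE counting unit is undefined.** SAP 9.2 refers to "multiple occurrences of the same event in the same period in the same subject", but SAP 3.4 names the screening, treatment and follow-up periods, and the rule only selects the worst severity.
- **The sodium reference is missing altogether.** SAP Table 3.4-1 sets the baseline before the Day 1 dose. Only later infusions are left open.

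**Conclusion.** The point holds as a reporting gap that is cheap to close. Followed as written, SAP 9 places AEs and sodium values above 147 mEq/L with onset at 8 mg in the escalated group, and no planned AE table, nor CT-10.6, separates them. This rests on the SAP text and table titles, because table shells are not shown.

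The 20% and 40% shares follow from the dosing rules for five full days. They are shares of dosing days, not of AEs, and are smaller once follow-up is included. The event shares rest on the assumption of equal, constant daily risk. The sodium effect depends on agreement between site and central values and on there being Day 3 escalators, of whom there may be none.

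A reader might infer that the split makes 16 mg look worse. The documents do not support a direction: 8 mg events are added to the escalated group, while the safety and sodium criteria keep some subjects with early problems out of it. The size and sign of any net distortion are unknown.

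**What to change.** 1. Keep the all-subject tables as the main safety result.
2. In SAP 9.2 and 9.3, add TEAE and sodium-event tables by dose at onset: 8 mg before any escalation, 16 mg, and 8 mg after reduction. Give subjects at risk and subject-days for each.
3. State how escalation-day AEs without an onset time and AEs in follow-up are assigned. For example, count the former under 16 mg and the latter under the last dose received. Any default can misplace some events, so list the events it affects.
4. Label the by-escalation split as descriptive and not a dose comparison.
5. For the count of rises above 10 mEq/L, state that the reference is the value immediately before each infusion. The withdrawal rule in Protocol 3.8.3.2 already uses the immediate predose value.

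The cost is SAP wording and a few tables. Infusion times, doses and AE onset dates are in the eCRF (Protocol 3.2.1, 5.2). Onset time is recorded for AEs of special interest and otherwise where possible. An AE that worsens in severity or seriousness is entered as a new AE, so it has its own onset. Central sodium arrives as an electronic file. No change in sample size follows.

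The downside is that the new tables also stay descriptive. Dose at onset is tied to treatment day, the 16 mg phase covers selected subjects, and there is some carry-over (Protocol 1.2.2 gives a tolvaptan half-life of 7.4 to 8.6 hours and 1.2- to 1.4-fold accumulation).

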### **9.1 Extent of Exposure**

Distributions of the number of subjects on each number of administration days will be calculated. Descriptive statistics of the number of administration days will be calculated. The number of subjects at each daily dose (8 or 16 mg) will be counted on each administration day. The combination of number of administration days for each daily dose will be summarized in a cross table.

### **9.2 Adverse Events**

All AEs will be coded by system organ class (SOC) and ICH Medical Dictionary for Regulatory Activities (MedDRA) preferred term (PT). The incidence of the following events will be summarized for all events, by SOC, and by PT.

- Treatment-emergent AEs (TEAEs)
- TEAEs by severity
- TEAEs with an outcome of death
- Serious TEAEs
- TEAEs leading to discontinuation of the IMP

If there are multiple occurrences of the same event in the same period in the same subject, the event with the highest severity will be selected. IMP-related TEAEs will be summarized in the same manner as shown above.

For TEAEs, a summary table will also be created for any TEAE that occurs in more than 2 subjects in any group.

